Drug Accountability: Once a randomization request has been completed and at least 2 days before the scheduled Baseline study visit), the Study Coordinator will coordinate dispensing of the study medication by the Research Pharmacy. The Research Pharmacy is responsible for determining which assignment (A or B) is active study-dose treatment (vitamin D₃ 3,333 IU/capsule to take daily except during the monthly study visit when 3,333 IU/capsule x 1 capsule and placebo x 1 capsule will be administered by study coordinator on-site or self-administered under direct observation by study coordinator during telehealth visit), and which assignment is control-dose treatment (placebo capsule to take daily except during monthly study visit when vitamin D₃ 50,000 IU/capsule x 2 capsules will be administered by study coordinator on-site or self-administered under direct observation by study coordinator during telehealth visit). Study medication labels will include the prescription number, subject ID, and randomization ID as recorded in the Research Pharmacy Medication Dispensing Log. The initial dose will be administered during the Baseline study visit after all the baseline procedures have been completed. Two capsules containing either study-dose (3,333 IU/capsule x 1 capsule and placebo x 1 capsule) or control-dose (vitamin D₃ 50,000 IU/capsule x 2 capsules) will be given orally. Capsules can either be swallowed or for those subjects who are unable to swallow capsules, contents of the capsules can be sprinkled in apple sauce or pudding and consumed in its entirety. Subjects will be instructed to take one capsule daily until the time of the next study visit. Subjects will be asked to count and dispose any unused capsules observed on video by study coordinator at the following monthly visit. The number of unused capsules will be recorded by the study coordinator in the Research Pharmacy Drug Return Log. These procedures will be repeated at each monthly study visit. Month 24 will serve as the Study Exit visit; study drug will not be administered or dispensed at this visit.

STUDY SUBJECTS

Inclusion criteria:

- 1) Diagnosis of sickle cell disease (Hb SS, Hb SC, Hb S-Beta-thalassemia)
- 2) Age 3-20 y/o

Exclusion criteria:

- 1) Patient unwilling or unable to provide written informed consent (and assent, if applicable)
- 2) Patient unable or unwilling to comply with requirements of the clinical trial
- 3) Participation in another clinical trial
- 4) Current diagnosis of rickets
- 5) History of hypercalcemia or diagnosis of any medical condition associated with hypercalcemia, including primary hyperparathyroidism, malignancy, sarcoidosis, tuberculosis, granulomatous disease, familial hypocalciuric hypercalcemia
- 6) Current use of corticosteroids, excluding inhaled steroids
- 7) Current use of anticonvulsants (phenytoin, phenobarbital, carbamazepine)
- 8) Therapy with thiazide diuretics or lithium carbonate
- 9) Known liver or renal disease
- 10) Patients taking medications for pulmonary complications of sickle cell disease not on a stable dose of medications, as defined by a change in medications or doses within the three months prior to study entry
- 11) Patients on chronic red blood cell transfusion therapy
- 12) Pregnancy

Subject Justification:

This study will enroll about 80 children and adolescents, ages 3-20 years, with sickle cell disease. Participation of children in the proposed research is essential to answer the research question, because pulmonary complications in sickle cell disease develop early in life. The study aims to determine whether vitamin D supplementation can reduce the risk of respiratory complications during childhood and prevent deterioration in lung function. The proposed research will predominantly include subjects of African origin, including African Americans and those from the Caribbean Islands (Dominican Republic, Puerto Rico, West Indies, Cuba, and Haiti), because sickle cell disease primarily affects people of African descent.³

Subject Randomization:

Within one month after screening procedures have been completed, subjects will be randomized. Using computer-generated randomization, participants with 25-hydroxyvitamin D concentrations of 5-60 ng/mL will be randomly assigned using randomly permuted blocks of size 2, 4 or 6 assignments with separate schema prepared for stratification by age (3-9 and 10-20), gender and hydroxyurea therapy. Randomization will be performed by the Research Pharmacy; all other research staff and participants will be blinded to allocation.

Subject Compensation:

Study participants will receive \$40 per monthly study visit, with the exception of the following 3 study visits: 1) Baseline/Randomization visit, 2) Month 12 visit, and 3) Month 24 Study exit visit, for which participants will receive \$100. The modest compensation will be provided to compensate for participant's time, transportation expense, and completion of study-required procedures. Compensation will be in the form of cash or gift card and paid in installment during each monthly visit. Participants will not be required to provide receipts for reimbursement. A total of \$540 per calendar year is compensated to each subject who completes all study-related visits.

STATISTICAL ANALYSIS PLAN

Our primary study hypothesis is that *daily* oral vitamin D₃ (cholecalciferol), 3,333 IU/d (0.083 mg/d), will reduce the annual rate of respiratory events (infections, exacerbations of asthma, and the acute chest syndrome) by 50% or more during Treatment Year 1 compared with *monthly* bolus oral vitamin D₃, 100,000 IU/mo (25 mg/d) as a control. As detailed above, control treatment with bolus administration of 100,000 IU (2.5 mg/d) oral vitamin D₃ monthly should provide an estimate of the annual rates of respiratory events that would be expected with placebo treatment.

Our primary study analysis will examine the annual rate of respiratory events (the sum of respiratory infections, asthma exacerbations and episodes of acute chest syndrome) in children with sickle cell disease randomized in a double-blind manner to the daily and monthly doses of oral vitamin D₃. The primary statistical analysis will be by "intention to treat" and will use a semiparametric regression method to estimate the between group difference in intensity (events per subject per unit of time at risk) with the assumption that covariates have a multiplicative effect on the mean and rate functions. This approach takes account of the skewed distribution of the respiratory events. The results of this analysis will be summarized as a regression parameter estimate, with the standard error of the estimate, a chi-square test with associated p-value, and a hazard ratio with confidence limits expressing the rate difference of the daily relative to the monthly group (as described in Lin, DY, Wei, LJ, Yang, I, and Ying, Z. "Semiparametric regression for the mean and rate functions of recurrent events," *J R Stat Soc Series B Stat Methodol*, 2000; 62:711–730).⁶³ This approach can adjust for group differences in time-independent covariates and estimate rate ratios at specific values of covariates and at specific times of follow up. The annualized rate of events and the average inter-event interval (in two-week intervals, the observation protocol) will be entered as time-independent covariates. After testing the initial hypothesis of overall group difference, we will sequentially test the between-treatment group differences in the study design enrollment criteria strata: age, gender and therapy (hydroxyurea). Secondary analyses using the same statistical framework will separately test the study hypotheses at the one-year time point. The functional form of covariates and proportional hazards assumptions will be checked for all models and cumulative hazard plots and cumulative residual plots will be used to display group differences in the evolution of events and model fit, respectively.

Subsidiary analyses will be made to examine a number of secondary study hypotheses with respect to the effects of vitamin D₃ on changes in pulmonary function and airway inflammation, and on immune system, but these comparisons have not entered into the sample size calculation. Data will be summarized as means \pm standard

deviation or as counts and proportions. Study Group differences in continuous measures at baseline will be compared using independent *t* tests and differences in dichotomous categorical measures at baseline will be compared using Fisher's exact test.

Sample size

For sample size estimation, we base our estimate of the annual rate of respiratory events on the rate observed in the earlier ViDAS-1 trial in our study population, a mean annual baseline respiratory event rate of 4.1. For our estimate of the treatment effect, we use the observed reduction in annual mean respiratory event rate in the earlier ViDAS-1 trial for *monthly* bolus oral vitamin D3, 100,000 IU/mo (2.5 mg/mo), from Treatment Year 1 to Treatment Year 2 from 4.28 ± 0.36 (SEM) to 1.49 ± 0.37 , or a decrease of about 65 percent. Using a conservative estimate of a treatment effect of 50 percent reduction in the rate of respiratory events as the minimal *clinically* significant difference to be detected, **26 subjects in each group will be sufficient to detect an effect size of this magnitude with a two-sided significance level of alpha = 0.025 and 90 percent power. Allowing for as much as a 15 percent loss of participants during the two-year study (due to clinical events, such as initiating chronic red blood cell transfusion therapy, failure of compliance or exclusion or withdrawal for any reason), then our sample size estimate is $26/0.85 = 31$ participants in each treatment group, or a total of 62 participants.** Although the secondary analyses planned have not entered into the calculation of the sample size required for the proposed study, the conservative specification for the treatment effect; 90 percent power; and a generous allowance for loss of participants, should help provide adequate power for subsidiary comparisons.

Annualized Event Rate and Inter-Event-Interval (IEI)

Individual participant rates of events during the treatment phase (Treatment Years 1 and 2) will be annualized by dividing the number of days of observation by 365.25. Individual participant inter-event-interval (IEI) will be the average of the number of days between the first day of observation and the day of the first event and the number of days separating the resolution of one event to the onset of the subsequent event. The treatment phase IEI will be calculated as the average of the number of days separating the resolution of one event to the onset of the subsequent event, the number of days from randomization to the first event, and the days between the last event and final day of study participation. If a participant is in the midst of an event episode on the day of randomization, the calculation of the average IEI will start with the date the event resolved.

Treatment Outcome Analysis

All primary and secondary outcome analyses will be performed under the intent-to-treat principle. Crude estimates of group differences in the annualized event rate and average inter-event-interval during Treatment Year 1 and Treatment Year 2 will be analyzed by linear mixed models for repeated measures with fixed effects for group, time and group-by-time interaction, and an AR(1) covariance structure. Analyses of secondary outcomes for pulmonary function testing will also use this approach. Further analysis of treatment group differences will be assessed using a variation of the Cox Proportional Hazards model with a counting process input of start and stop times for each event and the robust sandwich covariance estimator of Lin.⁶³ This approach models hazard for recurrence under the assumption of proportional mean processes and generates hazard ratios with 95% confidence intervals and Wald Chi-Square statistics for testing the null hypothesis. We will evaluate the influence of the event rate, average IEI as covariates and calculate between treatment group hazard ratios. We will also evaluate the influence of randomization stratifying variables as covariates of the estimate of the between treatment group difference: sex (female vs male), age (child vs adolescent) and hydroxyurea use (use vs non-use). For participants in each treatment group who withdraw from the study prior to completion of the protocol, we will repeat the primary intent-to-treat analysis with the subset of participants who completed the two-year study in a "per protocol" analysis. Finally, treatment group differences in adverse events of least grade 2 severity will be assessed with chi-square or Fisher's Exact test. We will only present comparisons of events where three or more instances are reported over the two-year treatment period.

DATA AND SAFETY MONITORING

Adherence to protocol: Conduct of the clinical trial will be in accordance with this new protocol for the ViDAS-2 study in our Investigational New Drug application. This protocol includes the appointment of a Clinical Trial Safety Officer to review laboratory results as they become available, and the formation of a Data and Safety Monitoring

Board (DSMB) consisting of an expert in pediatric sickle cell disease, a biostatistician, and a Pediatric Endocrinologist with expertise in vitamin D metabolism. The DSMB will meet bi-annually.

Safety monitoring and review plan: For the first month after initiation of study treatment, the Clinical Research Coordinator will telephone each study participant (or their parent or guardian) weekly to ask about any adverse experiences or any change from baseline status. To maintain blinding of participant treatment assignment during safety monitoring, a Clinical Trial Safety Officer, a physician expert in Pediatric Endocrinology and vitamin D metabolism, will be appointed to review laboratory results as they are performed during the course of the clinical trial to detect any abnormality requiring intervention. Abnormalities that require dose adjustment or other intervention will be reported immediately to the Sponsor-Investigator and summarized for annual reports to the U.S. Food and Drug Administration (FDA), the DSMB, and the Columbia University Institutional Review Board (CU IRB).

Reporting of adverse events: All identified Adverse Events will be reported to the Sponsor-Investigator. The Sponsor-Investigator will determine whether the event is *serious* or an *Unexpected Suspected Adverse Reaction* and requires expedited reporting. Serious Adverse Events (SAEs) that meet criteria for FDA and/or CU IRB reporting, i.e., unexpected, suspected to be related to study drug (FDA requirements), or unanticipated problems (CU IRB requirement) will be reported within 24 hours to the Sponsor-Investigator for review. Other SAEs that do not meet the above criteria will be reviewed by Clinical Trial Safety Officer with reports to the Sponsor-Investigator quarterly. The Sponsor-Investigator must also report SAEs that meet criteria for FDA and/or CU IRB reporting to the DSMB promptly within one week, while other SAEs that do not meet the above criteria will be reported to the DSMB Chair quarterly. The Sponsor-Investigator is required to report to the FDA serious, unexpected, suspected adverse event within 15 days, and within 7 days if fatal. A serious, unexpected suspected adverse reaction is a serious adverse event not previously observed with the drug and that has a reasonable possibility of having been caused by it. The CU IRB requires reporting of all Unanticipated Problems promptly and not later than one week, as well as during continuing annual review. An Unanticipated Problem is defined as any incident, outcome or experience involving risks to subjects or others in any human subject research that is unexpected, related or possibly related to research participation, and suggests that the research places subjects or others at a greater risk of harm (physical, psychological, economic or social harm) than was previously known or recognized. Adverse Events that do not meet the criteria of a SAE will be reported the DSMB during biannual review.

Clinical Trial Data and Safety Monitoring Board review: The Trial Statistician and Trial Epidemiologist will prepare a report for the DSMB at the end of Treatment Year 1 and Treatment Year 2. Data will be presented in a blinded fashion and study subjects will be identified only in the case of a safety concern. Biannual (and, if needed, more frequent) safety reviews will be conducted. Consideration for early termination of the trial will include: (i) failure of enrolled participants to meet entry criteria, (ii) differences in the baseline characteristics of the two study groups (despite gender- and age-stratified randomization), (iii) excessive or unbalanced loss of study participants, and (iv) other considerations to be determined by the DSMB.

Data management and quality: The Sponsor-Investigator or a designated Study Investigator will review all completed data collection forms biannually for protocol compliance and for completeness and accuracy of data. A statement of the results of this review will be included in the annual report to the FDA Orphan Products Program, in the annual IND report to the FDA, the CU IRB, and in the biannual reports to the Clinical Trial Data and Safety Monitoring Board and.

Reviews of clinical trial progress: Progress in the conduct of the clinical trial will be reviewed at least annually and more frequently as required by the FDA and the CU IRB, and biannually by the Clinical Trial Data and Safety Monitoring Board,

Records to be kept: Case Report Forms (CRF) will be provided for each subject. Subjects will not be identified by name on any study documents. After patient and subject identifiers have been replaced by study identifiers, the results of all clinical and laboratory assessments will be recorded on Case Report Forms for each subject. In a similar manner, demographic data and data from the medical history, physical examination will be recorded on Case Report Forms. All data on the Case Report Forms will be legibly recorded in black ink or typed. Corrections will be made by striking through the incorrect entry with a single line and then entering the correct information

adjacent to it. The correction will be initiated and dated by the Sponsor-Investigator or a designated, qualified staff member. Any requested information that is not obtained as specified in the protocol will have an explanation noted on the Case Report Forms as to why the required information was not obtained. Data for the Case Report Forms will be entered into a computerized database and entered into a Columbia University Certified Environment encrypted and protected with a strong password, in accordance with Columbia University encryption policies

Confidentiality of study data: The Sponsor-Investigator will be responsible for the accumulation and maintenance of appropriate data files and the preservation of the confidentiality and security of these files. The need for strict confidentiality of all study records will be emphasized to the staff of the study. Subjects will not be identified by name on any study documents and will be identified solely by a Study Identification Number. All reports and summaries prepared by the Investigator will be presented in such a way that no individual participant can be identified. The data collected in this study will remain under the control of the Investigator and will be kept confidential with the sole exception that Hospital or Government authorities may have access to records containing the identity of study volunteers. If publications result, volunteer names will not be used. All forms, computer tapes and diskettes will be kept in locked cabinets. All computerized files will be encrypted and protected with a strong password, in accordance with Columbia University encryption policies.

10.3 References cited:

2. Hassell KL. Population estimates of sickle cell disease in the U.S. *Am J Prev Med*. 2010;38(4 Suppl):S512-21. Epub 2010/04/02. doi: 10.1016/j.amepre.2009.12.022. PubMed PMID: 20331952.
4. Ware RE, de Montalembert M, Tshilolo L, Abboud MR. Sickle cell disease. *Lancet*. 2017. Epub 2017/02/06. doi: 10.1016/s0140-6736(17)30193-9. PubMed PMID: 28159390.

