IMMUNE SYSTEM CHANGES (aim 3)																										
T effector function																										
IL-4, IL-5, IL-13, IFN γ , IL-2		X						X				X				X				X						X
T regulatory function																										
IL-10, TGF- β		X				X						X			x				X						X	
Systemic inflammation																										
CBC/plts		X						X				X			X				X						X	
Serum CRP		X						X				X			X				X						X	
IL-1 α , IL-1 β , TNF α		X						X				X			X				X						X	

Abbreviations and explanations: Respiratory events: questionnaire for respiratory events during preceding two weeks; Oral vitamin D₃: 100,000 IU (2.5 mg) oral vitamin D₃ once monthly with daily placebo or daily oral vitamin D₃ (3,333 IU/d); Diet/Sun exposure: Block Calcium and Vitamin D screener questionnaire and sun exposure questionnaire; HRQL: child and parent reported; PedsQL™ Generic Core Scale, and PedsQL™ Sickle Cell Disease Module; PFT: Pulmonary function tests; Serum 25(OH)D: Serum 25-hydroxyvitamin D concentration; Serum D₃: serum concentrations of vitamin D₃, the parent compound; Ca: calcium; CMP: comprehensive metabolic panel; PO₄: phosphate; Mg: magnesium; VDBP: vitamin D-binding protein concentration; Urinary Ca, Cr: Urinary calcium and creatinine; Serum PTH: Serum intact parathyroid hormone; β-hCG: β- Human chorionic gonadotropin; T-effector function: T-helper 1,2 cytokines interleukin (IL)-10, 4,5,13, 2 and interferon (IFN) γ . T-regulatory function by cytokines IL-10, transforming growth factor (TGF) β ; Systemic inflammation assessed by CBC: complete blood count with leukocyte and platelet (plt) counts; Serum CRP: Serum high-sensitivity C-reactive protein; and assessed by IL-1 α , β , tumor necrosis factor(TNF) α . For all assessments, a protocol window of ± 7 days is specified.

LC-MSMS:

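### The primary hazard ratio is adjusted for each participant's own event rate and inter-event interval, which as defined are outcomes of treatment, so a true 50% reduction would appear as a ratio near 1

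*Combined protocol and SAP*

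**What the plan says.** The primary analysis paragraph of the Statistical Analysis Plan specifies a semiparametric proportional-rates model for recurrent respiratory events with robust variance. On covariates it says: "The annualized rate of events and the average inter-event interval (in two-week intervals, the observation protocol) will be entered as time-independent covariates". No period is given.

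The section on annualized event rate and IEI defines one rate only: "Individual participant rates of events during the treatment phase (Treatment Years 1 and 2) will be annualized". It then gives two IEI definitions. The first has no period label and averages the gaps between events with "the average of the number of days between the first day of observation and the day of the first event". The second is labelled: "The treatment phase IEI will be calculated as the average of the number of days separating the resolution of one event to the onset". It also takes in the time from randomization to the first event and from the last event to the end of participation.

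Treatment Outcome Analysis uses the same two quantities in both roles. As outcomes, in linear mixed models: "Crude estimates of group differences in the annualized event rate and average inter-event-interval during Treatment Year 1 and Treatment Year 2". As covariates, in the hazard-ratio models: "We will evaluate the influence of the event rate, average IEI as covariates and calculate between treatment group hazard ratios". Again the covariates carry no period.

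The one-year test inherits the specification: "Secondary analyses using the same statistical framework will separately test the study hypotheses at the one-year time point".

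**The concern.** An annualized rate over Treatment Years 1 and 2 is the participant's event count divided by follow-up time. The treatment-phase IEI is close to its reciprocal. Both are determined after randomization, both are affected by treatment, and both are functions of the events that the model is meant to explain. Adjusting for them asks whether the arms differ in event intensity among participants who had the same event intensity. The answer is close to no whatever the drug does.

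At stake are the primary hazard ratio and its chi-square test. A real benefit could be reported as no effect, while the mixed models of rate and IEI, which omit these covariates, show a clear group difference. Two analyses of the same trial would then contradict each other, and a choice between them made after unblinding would not be credible.

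**Working it through.** **1. Can the covariates be read as baseline values from the text?** Nothing in the SAP calls either one baseline or pre-randomization. The year of baseline event records in the General investigational plan belongs to ViDAS-1. For ViDAS-2, the Schedule of Study Evaluations explains the respiratory-events item as a "questionnaire for respiratory events during preceding two weeks". At the Sample size section's rate of 4.1 events per year:

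- One recall: 4.1 × 14 / 365.25 = 0.157 expected events; Poisson P(0) = exp(−0.157) = 0.85.
- Screening and randomization recalls combined: 0.314 expected events; P(0) = 0.73.

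That is too little to form an individual rate or IEI. A look-back through medical records is not ruled out, but none is specified.

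**2. Why the effect disappears.** With N events in follow-up T, the covariate is R = N/T. Then E(N | R, arm) = R × T in both arms, so once R is known the arm carries no further information on N. In a log-linear model R entered linearly does not match this identity exactly, so R alone leaves a small residual effect. Adding the IEI removes most of what is left.

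**3. The plan's own figure.** ViDAS-1 SEMs of 0.36–0.37 with n = 31 give SD = SEM × √31 = 2.00–2.06. For a difference of 4.1 × 0.5 = 2.05, two-sided alpha 0.025 and 90% power, n = 2(2.241 + 1.282)² SD² / 2.05² = 24–26 per group (26–27 with the t distribution). Then 26/0.85 = 30.6, so 31. The stated 26 and 31 reproduce. They do not depend on this point.

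**4. Simulation.** From the documents: 4.1 events per year in control, 50% reduction, alpha 0.025 two-sided, at least 7 days between counted events. For an effect confined to Year 1: 4.28 versus 2.14, then 1.49 in both arms. Assumed: gamma frailty variance 0.05, 0.25 and 0.5; 5-day event duration; IEI equal to follow-up for participants with no event; covariates entered linearly. The model is log-linear for the rate with sandwich variance, 1,000 replicates per setting, 26 per arm unless stated. The counting-process rows use 31 per arm, 15% random dropout and 500 replicates.

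| Analysis and true effect | Covariates | Ratio | Rejection |
|---|---|---|---|
| Two years, constant | none | 0.52–0.53 | 78–100% |
| | rate alone or IEI alone | 0.92–0.94 | |
| | rate and treatment-phase IEI | 0.99–1.00 | 4–9% |
| | rate and the unlabelled IEI, computed on treatment-phase data | 0.96–0.97 | |
| | one-year pre-randomization rate | 0.52–0.53 | 95–100% |
| Two years, Year 1 only | none | 0.65 | 39–80% |
| | both | 1.00 | about 2% |
| Counting process, constant | none | 0.52–0.53 | 86–100% |
| | both | 0.99 | 3–4% |
| Counting process, Year 1 only | none | 0.64–0.65 | 47–90% |
| | both | 0.99 | 2–4% |
| One-year test | none | 0.52–0.53 | |
| One-year test, Year 1 only | both, two-year window | 0.79–0.80 | 52–54% |
| One-year test, constant | both, two-year window | 0.99–1.00 | |
| One-year test | both, Year 1 window | about 1.00 | |

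The unadjusted ratios sit slightly above the nominal values because of the 7-day rule. It turns a rate r into r / (1 + 7r/365.25), so 4.1 becomes 3.80, 2.05 becomes 1.97, and the ratio is 0.52. The Year-1-only case gives (2.06 + 1.45) / (3.96 + 1.45) = 0.65.

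**5. Further runs.** A separately coded proportional-rates simulation (31 per arm, 15% early loss, 400 replicates, same frailty range) gave these two-year results:

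- no covariate: 0.49–0.50, rejection 84–99.8%;
- rate alone: 0.89–0.90, 12–27%;
- IEI alone: 0.91–0.93, 45–51%;
- both: 0.99, 4–7%;
- pre-randomization rate: 0.49–0.50, 98–99.8%.

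Another run at 26 per arm moved the ratio from about 0.52 to 0.99 and rejection from 83–99% to 6–14%. With no true effect (frailty 0.25) the ratio adjusted for both stayed at 1.00 with 3.7% rejection against a nominal 2.5%. The simulation standard error is √(0.025 × 0.975 / 400) = 0.8 points, so there is no clear false-positive excess.

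**The case against.** The best defence is that baseline covariates were intended. The SAP labels on-treatment quantities elsewhere and leaves these two unlabelled. A separate unlabelled IEI beside a labelled treatment-phase IEI suggests another phase. The sentence before the covariate sentence speaks of adjusting for group differences, which fits baseline imbalance. Participants come from the same centre's sickle cell program, so a record look-back is feasible. All of this stands as evidence of possible intent, and a true baseline covariate would carry no such bias. It does not supply a ViDAS-2 baseline rate, window or source, so the covariate cannot be built from the plan. Calling the covariates time-independent does not help either, because a whole-follow-up average is also one constant per participant.

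A second defence is that the first test may be unadjusted, since the SAP speaks of an initial overall test and Treatment Outcome Analysis speaks only of evaluating the covariates' influence. But the initial test is contrasted with tests within strata and is nowhere called unadjusted, and the softer wording does not override a flat statement that the covariates go into the model. A text that allows either a ratio near 0.5 or one near 1 has not prespecified the primary result.

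Two limits are fair. The near-null figures require treatment-phase values with both covariates entered. And the one-year test with two-year covariates and a Year-1-only effect is attenuated, not erased.

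**Conclusion.** The concern holds. As written, the primary hazard ratio is conditioned on its own outcome. With a constant 50% reduction over two years, the ratio moves from about 0.5 to 0.99–1.00 when both covariates are entered, and rejection drops from 77% or more to 14% or less in every run. With an effect in Year 1 only, it moves from 0.64–0.65 to 0.99–1.00. The exact figures depend on the assumed frailty, event duration, dropout pattern and handling of participants with no events; the direction did not change in any setting. The harm is loss of the effect estimate and of power, not a clear rise in false positives. The finding concerns the written specification and does not show what the authors intended. It must be fixed before unblinding.

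**What to change.** Delete the treatment-phase event rate and IEI as covariates from the primary model and from the hazard-ratio models in Treatment Outcome Analysis, and keep both as outcomes or descriptive summaries. State that the primary hazard ratio is adjusted only for pre-randomization variables. The stratification factors under Subject Randomization (age group, sex, hydroxyurea) are the natural set; including them is good practice but is not itself what cures the defect. Apply the same covariate rule to the one-year test.

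If a prior event rate or IEI was intended, say so, and give its pre-randomization window and data source. Label the first IEI definition with its period or delete it. In the same edit, correct the annualization sentence: days of observation divided by 365.25 gives years of follow-up, and the rate is the event count divided by that.

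Deletion costs SAP wording only. A baseline rate would need a defined look-back through existing medical records. Neither needs more participants.
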